13.2.5.2. Multiplicity

It is planned to use statistical analysis methods, which incorporates corrections for multiplicity. When needed, corrections for multiplicity will be justified and performed according to Bonferroni. Overall alpha-level will be controlled and will not exceed 0.05

13.3 Interim Analyses

No interim Analysis is planned in the study

13.4 Determination of Sample Size

Sample size was calculated for the primary objective of the study: to estimate the effect of Edarbi® treatment on blood pressure for patients with increased weight or obesity. This estimation will be conducted with 95% confidence interval construction. Sample size was calculated using SAS 9.3 proc power procedure (Confidence Interval for Paired Mean Difference) for following parameters (fixed scenario elements):

Fixed Scenario Elements	
Distribution	Normal
Method	Exact
Alpha	0.05
CI Half-Width	1
Standard Deviation	17.79
Correlation	0.4375
Nominal Prob(Width)	0.9
Number of Sides	2

Prob Type	Conditio nal
------------------	-------------------------

Where the distribution is assumed to be normal, alpha specifies the level of significance, Nominal Prob (Width) specifies the desired probability of obtaining a confidence interval half-width less than or equal to the value specified as CI Half-Width. Half-width of the desired confidence interval was set to 1 mm Hg. Standard deviation and correlation coefficient were estimated by pooling recent studies data [12, 13, 14, 19, 20] for clinic Systolic Blood Pressure after at least 6 weeks of antihypertensive treatment with azilsartan medoxomil. Pooled effect estimation (clinic SBP difference at the end of the treatment from baseline SBP value) is -17.311 with pooled SD of 17.7887, which corresponds to the standardized difference of -0.9731 and correlation coefficient of 0.4375. For the denoted scenario, it is required to receive data from at least 1437 patients before-after the treatment.

Computed N Pairs	
Actual	N
Prob(Width)	Pairs
0.903	1437

Taking into account a possible dropout of 25%, it is recommended to enrol at least 1916 patients into the study.

According to the reference studies [24-29], the SD for effect for DBP is less than the SD for SBP, so the denoted number of patients will be sufficient for the corresponding secondary outcomes.

14 Reports

A Non-Interventional Study Report based on the results obtained will be prepared and submitted to the Sponsor for distribution. The Final Study Report should be available within one year from collection of the last data point, and the participating sites should be informed about the results when the report is finalised. Composed the study report should be provided to the IEC.

15 Publications

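### The planning correlation of 0.4375 is the standardised difference converted to an effect-size r, not a baseline-to-V4 correlation, so the 1437 pairs and the 1 mm Hg precision rest on a wrong input

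*Protocol*

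**What the plan says.** Protocol section 13.4 plans for precision. The method is named as follows: "Sample size was calculated using SAS 9.3 proc power procedure (Confidence Interval for Paired Mean Difference". The target is a two-sided 95% interval, and "Half-width of the desired confidence interval was set to 1 mm Hg", to be met with probability 0.9 on the conditional definition. The table of fixed inputs lists a standard deviation of 17.79 and a correlation of 0.4375.

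On where these two inputs come from, the section says that they "were estimated by pooling recent studies data [12, 13, 14, 19, 20"]. It then reports that the pooled effect, described as the difference between end-of-treatment and baseline clinic SBP, "is -17.311 with pooled SD of 17.7887", "which corresponds to the standardized difference of -0.9731 and correlation coefficient of 0.4375". The result is 1437 pairs (actual probability 0.903) and, after 25% dropout, 1916 patients. A closing sentence carries the number over to diastolic pressure because "the SD for effect for DBP is less than the SD for SBP".

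No other within-patient correlation appears in the protocol. SAP section 2.4 has no sample-size calculation of its own.

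**The concern.** The paired-mean procedure builds the SD of the difference from two quantities: the SD of one reading, and the correlation between a patient's baseline and final readings. A mean change and one SD cannot supply that correlation. Section 13.4 nevertheless presents 0.4375 as the counterpart of a standardised difference computed from exactly those two figures. A correlation obtained that way is a rescaled effect size, and it would change with the size of the drug effect whatever the agreement between visits.

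The SD is unclear too. The text attaches 17.7887 to the change in SBP, and the diastolic sentence also speaks of the SD of the effect. In the table the same figure sits where the procedure expects the SD of a single reading.

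The number of pairs, the enrolment target, the 90% assurance and the statement that the sample suffices for DBP all depend on these inputs.

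**Working it through.** **Inputs, all from Protocol section 13.4:** mean change -17.311; SD 17.7887 (entered as 17.79); correlation 0.4375; half-width 1 mm Hg; two-sided alpha 0.05; conditional probability 0.9; dropout 25%.

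**Step 1: reproduce the plan.** The procedure uses SD_diff = SD × √(2(1 − ρ)) = 17.79 × √(2 × 0.5625) = 17.79 × √1.125 = 18.869. The required number is the smallest n for which the half-width t(0.975, n−1) × s/√n is at most 1 with probability at least 0.9, given that the interval covers the true mean. At n = 1436 the probability is 0.8993, and at n = 1437 it is 0.9027. This matches the printed 1437 and 0.903. Then 1437/0.75 = 1916. The arithmetic is right, and it confirms that 0.4375 was used as the within-patient correlation.

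**Step 2: where 0.4375 comes from.** d = -17.311/17.7887 = -0.9731. The conversion to an effect-size r is |d|/√(d² + 4) = 0.9731/√(0.9469 + 4) = 0.9731/2.2242 = 0.4375. It agrees with the entered value to four decimals, with the sign dropped.

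**Step 3: if 17.79 is the SD of the change.** No correlation is needed. The same method with SD_diff = 17.79 gives 1281 pairs, and 1281/0.75 = 1708 enrolled. The planned figures are therefore larger by 1437 − 1281 = 156 pairs and 1916 − 1708 = 208 patients. The expected half-width at 1437 pairs is about 1.96 × 17.79/√1437 = 0.92 mm Hg, against 0.98 with SD_diff = 18.869.

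**Step 4: if 17.79 is the SD of a single reading.** The documents give no true correlation, so the range below is an assumption.

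| Assumed ρ | SD_diff | Pairs needed | Enrolled (÷ 0.75) | Half-width at 1437 pairs | P(half-width ≤ 1) at 1437 |
|---|---|---|---|---|---|
| 0.2 | 22.50 | 2027 | 2703 | 1.16 | about 0 |
| 0.3 | 21.05 | 1779 | 2372 | 1.09 | about 0 |
| 0.4 | 19.49 | 1530 | 2040 | 1.01 | 0.33 |
| 0.4375 (plan) | 18.87 | 1437 | 1916 | 0.98 | 0.90 |
| 0.5 | 17.79 | 1281 | 1708 | 0.92 | about 1 |
| 0.6 | 15.91 | 1031 | 1375 | 0.82 | about 1 |
| 0.7 | 13.78 | 780 | 1040 | 0.71 | about 1 |

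The row for 0.5 equals step 3 because √(2 × 0.5) = 1.

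**Step 5: the cited sources.** By title, references 12, 13, 14, 19 and 20 are a hypertension guideline, a population survey, country profiles of noncommunicable disease, a paper on uncontrolled hypertension and an epidemiological study of resistant and uncontrolled hypertension. None is identifiable as an azilsartan study, so the reader cannot trace either input.

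**The case against.** The section says that the correlation was estimated by pooling, and the pooled data are not shown, so the conversion is inferred rather than documented. The sign was also dropped on the way. The inference is still strong: the match holds to four decimals, the wording ties the coefficient to the standardised difference, and no separate correlation is reported.

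A better objection concerns consequence. On the reading the text favours, with 17.7887 as the SD of the change, the plan is conservative. At 1437 pairs a half-width of at most 1 mm Hg is practically certain, and the expected half-width differs from the planned one by only about 0.06 mm Hg, in the safe direction. The poor figures in step 4 need both the other reading of the SD and a low correlation, and the documents supply neither. This stands, and it means that the direction of the error is not established.

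The reference numbers may simply be stale. Section 8.9 cites 25 and 34 for the personal-data laws, although the Russian law is reference 29, and section 10.9 cites 21 for a guideline listed as reference 6. The citations therefore show a traceability gap; they do not show that nothing was pooled.

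Finally, the reported interval will come from observed changes (Protocol 13.2.2, SAP 9.1), and the planning correlation plays no part in it. This is also correct. The defect lies in the justification of the sample size and of the stated precision.

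**Conclusion.** The concern holds. The calculation is correct for its inputs, but 0.4375 is an effect-size r used as a within-patient correlation, and it cannot support the stated precision. If 17.7887 is the SD of the change, the target is about 12% too high (1437/1281 = 1.12) and the half-width goal is met with room to spare. If it is a single-reading SD, the 90% assurance is unsupported: it fails for a true correlation clearly below 0.4375 and is exceeded above it. The range of 0.2 to 0.7 is assumed. The validity of the final analysis is not affected. The section should be corrected because it states a sample size and a precision that do not follow from a proper input.

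**What to change.** In Protocol section 13.4:

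- Remove 0.4375 and state whether 17.7887 is the SD of the change or of a single reading.
- If it is the SD of the change, size on it directly with a one-sample interval. Either restate the requirement as 1281 pairs and 1708 enrolled, or keep 1916 and give the expected half-width at 1437 pairs as about 0.92 mm Hg.
- If it is a single-reading SD, say so. Give a sourced baseline-to-V4 correlation if there is one, and in any case report the half-width at 1437 pairs over a stated range of correlations.
- Cite the studies actually pooled, and recheck the diastolic sentence on the same basis.

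The cost is a reworded section and one rerun of the procedure. No extra patients are needed, because the precision statement can be restated at the planned size. More would be needed only if the SD is that of a single reading, the correlation is below 0.4375, and the sponsor keeps the 1 mm Hg goal at 90%.

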15.1 Publication and Disclosure

During the study, only the sponsor may make study information available to other study investigators or to regulatory agencies, except as required by law or regulation. Except as

otherwise allowable in the study site agreement, any public disclosure (including publicly accessible websites) related to the protocol or study results, other than study recruitment materials and/or advertisements, is the sole responsibility of the sponsor.

The sponsor may publish any data and information from the study (including data and information generated by the investigator) without the consent of the investigator. Manuscript authorship for any peer-reviewed publication will appropriately reflect contributions to the production and review of the document. All publications and presentations must be prepared in accordance with this section and the study contracts. In the event of any discrepancy between the protocol and the study contracts, the study contracts will prevail.

The sponsor aims to have the results of this study published and acknowledges the right of the participating sites to publish results from this study. The sponsor has the right to use the data and results for regulatory purposes and for internal presentation within the company and to partners

2. PROTOCOL SUMMARY

2.1 Study design and conduct

This is an international, prospective, multicentre, non-interventional, observational study.

The observational study schematic:

For study details and study assessment's schedule see the Protocol of the Study.

Term	Baseline visit (V1)	Observational visit (Month 1)	Observational visit (Month 3)	Final Observational visit (Month 6)
Inclusion/exclusion criteria	X			
Signed Informed consent form	X			
Date of visit	X	X	X	X
Demographic information	X			,
Medical history (incl. risk factors, prior diseases, prior HTN therapy etc)	X			
Body Mass Index (BMI)	X	X	X	X
Physical examination and vital signs*	X	X	X	X
HTN therapy (drugs, doses)	Х	X	X	X
Laboratory tests and instrumental exams*	X	x	x	x
Concurrent medical conditions	X			

Concomitant medication	X X X
Adverse events	X X X

* All examinations (physical examination and vital signs, laboratory tests and instrumental exams) are done in accordance with clinical routine practice and physician's decision. Instrumental exams are measurement of blood pressure, hard rate, ECG, 24-hour ambulatory blood pressure monitoring. All examinations should be registered in the CRF only if they are done in routine practice.

2.2 Study objectives

2.2.1 Primary objective

1. To evaluate the effect of Edarbi® on clinic systolic blood pressure (SBP) among hypertensive (HTN) patients with overweight or obesity (Month 6).

2.2.2 Secondary objectives

- 1. To evaluate the effect of Edarbi® on clinic diastolic blood pressure (DBP) among HTN patients with overweight or obesity (Month 6);
- To evaluate the proportion of overweight or obese patients who respond to Edarbi® therapy (defined as decrease of SBP≥ 20 mm Hg or decrease of DBP≥10 mm Hg) (Month 6);
- 3. To evaluate the proportion of overweight or obese patients who achieved target BP (defined as SBP<140 and DBP<90mm Hg) (Month 6);
- To evaluate the effect of Edarbi® on clinic SBP among HTN patients with overweight or obesity in subgroups of patients: BMI (overweight, obese), impaired glucose tolerance, metabolic syndrome, diabetes mellitus (Month 6);
- 5. To evaluate the effect of Edarbi® on clinic DBP among HTN patients with overweight or obesity in subgroups of patients: BMI (overweight, obese), impaired glucose tolerance, metabolic syndrome, diabetes mellitus (Month 6);
- To evaluate the proportion of overweight or obese patients who achieve target BP (SBP<140 mm Hg, DBP<90 mm Hg) in subgroups of patients: BMI (overweight, obese), impaired glucose tolerance, metabolic syndrome, diabetes mellitus (Month 6).

2.2.3 Safety objectives

1. To describe AE characteristics.

1.	1, Company Confidential Informa	tion
2.	2.	
3.	3.	
4.	4.	
5.	5.	
6.	6.	
7.	7.	
8.	8.	

2.2.4 Exploratory objectives

2.3 Study variables

2.3.1 Efficacy variables

Primary outcome variables:

1. Change from baseline in clinic SBP on Edarbi® therapy (Time Frame: Baseline and Month 6). Secondary outcome variables:

- 1. Change from baseline in clinic DBP on Edarbi® therapy (Time Frame: Baseline and Month 6);
- Proportion (%) of patients who respond to Edarbi® therapy (defined as decrease of SBP≥ 20 mm Hg or decrease of DBP≥10 mm Hg; Time Frame: Baseline and Month 6);
- Proportion (%) of patients who achieve target BP <140 mm Hg (defined as SBP<140 and DBP<90mm Hg) (Time Frame: Baseline and Month 6);
- 4. Changes from baseline in clinic SBP in subgroups of patients: BMI (overweight, obese), impaired glucose tolerance, metabolic syndrome, diabetes mellitus (Time Frame: Baseline and Month 6);
- Changes from baseline in clinic DBP in subgroups of patients: overweight, obese (stages I-III), impaired glucose tolerance (yes, no), metabolic syndrome (yes, no), diabetes mellitus (yes, no) (Time Frame: Baseline and Month 6);
- Proportion (%) of patients who achieve target BP (SBP<140 mm Hg, DBP<90 mm Hg) in subgroups of patients: overweight, obese (stages I-III), impaired glucose tolerance (yes, no), metabolic syndrome (yes, no), diabetes mellitus (yes, no) (Time Frame: Baseline and Month 6).

All variables listed above will be evaluated within final study analysis and within interim study analysis. It's planned that interim statistical analysis of study data will be performed as soon as470 first study patients have completed the study by achieving final study visit or discontinuing their participation

2.3.2 Safety variables Safety Outcome variables:

1. Incidence and type of adverse events.

Safety outcomes will be evaluated within final study analysis and within interim study analysis. It's planned that interim statistical analysis of study data will be performed as soon as 470 first study patients have completed the study by achieving final study visit or discontinuing their participation

2.3.3 Other variables of interest Exploratory outcome variables:

Company Confidential Information

2.4 Sample size and power

This particular analysis is performed for the subgroup of study participants from Republic of Kazakhstan. There was no formal power or sample size calculation planned in the protocol for this subgroup, only the total sample size (taking Russian Federation and Republic of Kazakhstan as one sample for analysis). Therefore, certain results may be unavailable or not applicable due to the small sample size of subgroup from Republic of Kazakhstan.

3. DATA ANALYSIS CONSIDERATIONS Overall analysis frame

This study is observational and epidemiological methods will be employed for data analyses. Descriptive analysis will be performed of all collected data, i.e. all data listed in section 2.3 ("Study variables"), except for the data collected only for the purpose of data cleaning.

The primary and secondary outcomes of the study are presented in section 2.3.1 ("Efficacy variables").

Summary of study data

All continuous variables will be summarized using the following descriptive statistics: n (nonmissing sample size), mean, standard deviation, median, 25 percentile, 75 percentile, maximum and minimum. The frequency and percentages (based on the non-missing sample size) of observed levels will be reported for all categorical measures. For variables marked "binary" exact (Clopper-Pearson) 95% confidence intervals will be calculated where appropriate. For categorical variables with more than 2 categories 95% confidence intervals will be calculated using Goodman's method or other appropriate (e.g. Sison and Glatz) method.

In general, all data will be listed, sorted by site and patient, and when appropriate by visit number within patient. All summary tables will be structured with a column for each cohort in the increasing order and will be annotated with the total population size relevant to that table/dose cohort, including any missing observations.

Baseline data

The baseline visit is defined as the last observations collected prior to administration of the study drug.

Analysis of data from republic of Kazakhstan

All the study objectives listed in the section 2.2. of the current SAP will be evaluated within the final study analysis study analysis of data obtained in the Republic of Kazakhstan. As this analysis was not initially planned and accordingly was not formally powered, some of the endpoints and subgroup analysis can be not applicable given the actual amount of data collected. If the analysis is not possible, this will be noted in the corresponding section of the statistical analysis report, with the reasons listed.

Definitions of study-specific derived variables

In accordance with the Protocol of the Study, derived variables will be calculated using following conventions:

Target Blood Pressure (BP) – target BP for all categories of patients is <140/90 mm Hg, except of patients with diabetes in whom target BP is <140/85 mm Hg.

Target Diastolic Blood Pressure (DBP) –, target DBP for all categories of patients is <90 mm Hg, expect of patients with diabetes in whom target BP is <85 mm Hg

Target Systolic Blood Pressure (SBP) –, target SBP for all categories of patients is <140mm Hg

BP response – decrease of SBP≥ 20 mm Hg or decrease of DBP≥10 mm Hg

Overweight – elevation of body mass index (BMI) is from 25 to 30 (25 <= BMI < 30)

Obesity – elevation of BMI >= 30. Obesity is divided for 3 classes according to severity.

Class of obesity	BMI
Obesity class 1	$30 \ge BMI \ge$
	34.9
Obesity class 2	$35 \ge BMI$
	≥39.9
Obesity class 3	$BMI \ge 40$

Metabolic syndrome – according to the definition of the Russian Ministry of Health for the management of hypertension (HTN), metabolic syndrome is diagnosed in the presence of main criterion and 2 any additional criteria listed below:

Main Criterion	Men	Women
waist circumference	≥94 cm	≥80 cm
Additional Criteria	Men	Women
low-density lipoprotein cholesterol	>3.0 mmol/l	>3.0 mmol/l
high-density lipoprotein cholesterol	<1.0 mmol/L	<1.2 mmol/L
Triglycerides	>1.7 mmol/L	>1.7 mmol/L
impaired glucose tolerance	post-load plasma glucose 7.8	post-load plasma glucose 7.8
(post-load plasma glucose)	- 11.0 mmol/L	- 11.0 mmol/L
fasting glucose	6.1 - 7.0 mmol/l	6.1 - 7.0 mmol/l

Body Mass Index (BMI) Calculation

BMI will be calculated using the formula provided below, rounded to 2 decimals: $BMI = weight [kg]/height [m]^2$

4. CLINICAL DATABASE Database for final analysis

A snapshot of the clinical database will be generated after all subjects have completed through the final visit of the study or discontinued participation in the study. Snapshot for final analysis will be performed after database lock according to relevant CRO's Standard Operating Procedure (SOP) for database lock and data extraction. All tables, figures, and listings (TFLs) described in this SAP will be generated on this snapshot of the database.

Database for interim analysis

As soon as first 470 study patients have completed through final visit of the study or discontinue their participation a snapshot of the clinical database will be generated. The snapshot of the database will be performed in accordance with Standard operating procedures of CRO responsible for Data collection and data management. All tables, figures and listings described in this SAP will be generated on this interim snapshot of the database

Database for final analysis in the Republic of Kazakhstan

Analysis, according to this particular Statistical Analysis Plan, will be performed only for the data obtained in the Republic of Kazakhstan.

A snapshot of the clinical database will be generated after all patients have completed through the final visit of the study or discontinued participation in the study. Snapshot for final analysis will be performed after database lock according to relevant CRO's Standard Operating Procedure (SOP) for database lock and data extraction. Statandocs will receive the data related to study participants from Republic of Kazakhstan only, via the agreed communication channels.

All tables, figures, and listings (TFLs) described in this SAP will be generated on this snapshot of the database (with data from Republic of Kazakhstan only).

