10.3. Data collected on the Baseline visit

Baseline visit is a visit after physician makes a decision to prescribe Edarbi® for HTN treatment. It means that investigator inform patient about the study only after taking decision about strategy of HTN treatment.

Data to be collected:

- Date of visit (day, month, year)
- Date of Informed consent form signing (day, month, year)
- Compliance with Inclusion/exclusion criteria
- Demographic information: sex, date of birth, ethnicity, region of residence (city, town etc)
- Medical history:
 - History of HTN
 - Duration of HTN/first diagnosed
 - Presence of HTN target organ damage
 - Risk factors of cardiovascular disease (smoking, dyslipidaemia, glucose intolerance, obesity, abdominal obesity, family history of cardiovascular disease,)
 - Cardiovascular diseases history:
 - established cardiovascular diseases (coronary artery disease, chronic heart failure, arrhythmias, peripheral artery diseases, ischemic heart disease etc.)
 - history of cardiovascular events (myocardial infarction, stroke, etc.)
 - Alcohol use
- Diagnose of HTN: grade, stage, risk.
- Physical examination and vital signs: height (cm), weight (kg), waist circumference (cm), body mass index, systolic and diastolic blood pressure (position, time, values), heart rate, physical inactivity

- HTN treatment:
 - previous HNT-treatment (if applicable),
 - reason(s) for discontinuation of previous HNT-treatment (if applicable),
 - monotherapy/combination treatment,
 - Edarbi® dosage regimen,
 - other HTN co-medications: INN, trade name, dosage regimen (if applicable).
- Laboratory data (last available measurements, if done within routine practice):
 - total cholesterol,
 - triglycerides,
 - low-density lipoproteins,
 - high-density lipoproteins,
 - blood glucose,
 - serum creatinine,
 - urea,
 - glycated haemoglobin
- Concurrent medical conditions (diabetes mellitus, chronic kidney disease, chronic obstructive pulmonary disease, etc.)
- Concomitant medication: INN, trade name, dosage regimen (single and total daily dose), duration of treatment, indication for administration
- Adverse events: seriousness, severity, causality, start and stop dates, action, outcomes

10.4. Data collected on the Observational visits 2, 3 and 4

Data to be collected:

- Date of visit (day, month, year)
- Diagnose of HTN: grade, stage, risk.

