9.3 Additional methods of analysis

9.3.1 Subgroup analyses. Primary efficacy variable as well as the variables listed at the items 1-10 in the section 9.2 will be analyzed both in general population and in the following subgroups (if applicable):

- patient sex (male/female);
- patient age (60 or more, <60 years old);
- BMI (normal (<25); overweight (25-30), obese (>30_) and according to grade of obesity (grade I 30-34,9; Grade II 35-39,9; Grade III ≥40)
- metabolic syndrome (yes, no),
- diabetes mellitus (yes, no),
- diabetes mellitus, impaired glucose tolerance or normal glucose metabolism
- subgroups with different eGFR according to CKD-EPI (eGFR <30; 30-59 and >=60);
- subgroups according to previous antihypertensive treatment (treated/not treated and treated patients according to class of antihypertensive treatment used before initiation of Edarbi); the group of patients who was treated with RAAS blocker monotherapy and the group of patients who was treated with combination of RAAS blocker and diuretic and the group of patients who was treated with RAAS blocker and Calcium channel blocker to be described separately.
- patients with newly diagnosed hypertension
- The subgroup of patients with isolated systolic hypertension (patients not treated with antihypertensive treatment before the study who has SBP ≥140 mm Hg and DBP <90 mmHg at visit 1).
- diabetes mellitus or metabolic syndrome or nothing;
- Subgroup of Patients with Chronic heart failure and patients without chronic heart failure in diagnosis
- Subgroups according to risk factors: smokers/non-smokers; family history of cardiovascular disease (yes/no)
- Subgroups according to target organ damage by HTN (yes/no; if yes according to organs involved (heart, kidney, brain, eyes, vessels).

- Subgroups according to antihypertensive treatment initiated at baseline level: monotherapy with azilsartan and patients receiving combination therapy with azilsartan (both in general and according to type of used combination (double therapy; triple therapy, other) and per classes of used in combination))

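### The metabolic-syndrome rule stops counting glucose above 7.0 (fasting) or 11.0 (post-load) mmol/L, so patients with diabetes are split between the 'yes' and 'no' subgroups by lipids and glucose control

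*SAP*

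**What the plan says.** Protocol 4.2 and SAP section 3 (study-specific derived variables) print the same table and attribute it to the Russian Ministry of Health. The rule is that "metabolic syndrome is diagnosed in the presence of main criterion and 2 any additional criteria listed below". The main criterion is waist circumference, at least 94 cm in men and 80 cm in women. The five additional criteria (mmol/L) are:

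- LDL cholesterol above 3.0
- HDL cholesterol below 1.0 (men) or 1.2 (women)
- triglycerides above 1.7
- "post-load plasma glucose 7.8" up to 11.0
- fasting glucose 6.1 to 7.0

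SAP 2.3.1 uses the result as a subgroup factor for three secondary outcomes (change in SBP, change in DBP, target BP). For the last two it is written out as "metabolic syndrome (yes, no), diabetes mellitus (yes, no) (Time Frame: Baseline and Month 6". SAP 9.3.1 applies the same split to the primary variable, and SAP section 11 asks for a between-subgroup p-value. SAP 9.2, item 6, reports the percentage of patients with metabolic syndrome.

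Diabetes is collected separately in protocol 10.3, under "Concurrent medical conditions (diabetes mellitus, chronic kidney disease, chronic obstructive pulmonary disease, etc", and is not an input to the rule. Laboratory values are "Laboratory data (last available measurements, if done within routine practice"; the list contains blood glucose, with no fasting label and no post-load test.

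**The concern.** A severity marker in a classification rule would normally be one-sided, as the three lipid criteria are. Here both glucose markers switch off above an upper limit, and no clause counts higher glucose, known diabetes or antidiabetic treatment. Diabetes is not an exclusion criterion, and patients with it are analysed as a subgroup.

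The consequence is a reversal. For a patient who needs the glucose criterion to qualify, worse glucose changes the class from 'yes' to 'no'. Patients with diabetes then fall on either side of the split according to how many lipid criteria they meet and how well glucose was controlled at the last measurement available at V1. A difference between the 'yes' and 'no' subgroups, or its absence, would partly reflect that sorting, and the reported percentage with metabolic syndrome would be lower than under an uncapped rule.

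**Working it through.** **1. The rule on single patients.** Inputs: the table in SAP section 3. Take a patient who meets the waist criterion and exactly one lipid criterion, with no post-load test.

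- Fasting 6.5: one lipid + one glucose = 2 additional criteria, so 'yes'.
- Fasting 9.0: one lipid + none = 1 additional criterion, so 'no'.
- Fasting 9.0 with post-load 9.0: one lipid + one glucose (post-load) = 2, so 'yes'. This route needs a post-load result, which protocol 10.3 does not list.
- Any glucose with two or three lipid criteria: 'yes'.

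**2. The rule over a grid.** Waist met; 0-3 lipid criteria; fasting 5.5, 6.5 or 8.0; post-load not done, 7.0, 9.0 or 13.0. That is 4 × 3 × 4 = 48 profiles. The printed rule was compared with the same rule without upper limits (fasting at least 6.1, post-load at least 7.8, each row still counting separately).

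- 7 profiles change from 'no' to 'yes'; none changes the other way.
- 3 of the 7 have no lipid criterion and 4 have exactly one. All have fasting 8.0, post-load 13.0, or both.
- Nothing changes with two or three lipid criteria.

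These are counts of illustrative profiles, not proportions of patients.

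**3. A rough size.** The documents give no lipid or glucose distribution, so this rests on assumptions: prevalence of high LDL a = 0.3-0.6, low HDL b = 0.2-0.4, high triglycerides c = 0.35-0.5, independent, waist criterion met, no post-load test.

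P(exactly one) = a(1−b)(1−c) + (1−a)b(1−c) + (1−a)(1−b)c

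This is linear in each prevalence, so its extremes lie at the corners:

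| a, b, c | exactly one | two or more |
|---|---|---|
| 0.3, 0.2, 0.35 | 0.443 | 0.193 |
| 0.3, 0.2, 0.5 | 0.470 | 0.250 |
| 0.3, 0.4, 0.35 | 0.446 | 0.281 |
| 0.3, 0.4, 0.5 | 0.440 | 0.350 |
| 0.6, 0.2, 0.35 | 0.476 | 0.316 |
| 0.6, 0.2, 0.5 | 0.440 | 0.400 |
| 0.6, 0.4, 0.35 | 0.422 | 0.422 |
| 0.6, 0.4, 0.5 | 0.380 | 0.500 |

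So about 38-48% of above-range patients who meet the waist criterion would be 'no' only because of the upper limit.

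Protocol 5.1 gives 13% diabetes among patients with uncontrolled hypertension. Assume 50-80% of them are above range:

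- Low: 0.13 × 0.5 × 0.380 = 0.025
- High: 0.13 × 0.8 × 0.476 = 0.050

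That is roughly 2.5-5% of patients.

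**4. The Kazakhstan analysis.** SAP 2.4 and section 4 restrict this SAP to Kazakhstan data. Protocol 7.2 plans about 10 of about 90 sites there. If sites enrol equally (an assumption), 1437 × 10/90 ≈ 160 patients with data. Then 160 × 0.025 ≈ 4 and 160 × 0.050 ≈ 8.

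**The case against.** The strongest defence is that this is an adopted definition, printed identically in both documents and attributed to a national source that cannot be consulted here. The bands may be deliberate, with intermediate glucose counted in metabolic syndrome and diabetes handled as its own class. SAP 9.3.1 supports that reading to a degree, because it also lists diabetes yes/no, a split by glucose metabolism, and "diabetes mellitus or metabolic syndrome or nothing". This stands as a reason not to overwrite the protocol's definition. It does not remove the effect, because the yes/no split remains and does not separate diabetes cleanly: patients with diabetes who meet two lipid criteria, or one lipid criterion with fasting glucose 6.1-7.0, are still 'yes'.

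A second objection is that unlabelled or missing glucose is the larger practical problem. That also stands. It limits what any glucose threshold can do, and it leaves recorded diabetes as the one extra input that can be used as the data are listed.

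Three stronger readings are tempting, and the documents do not support them.

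- A reader might infer that patients with diabetes are classed 'no' as a group. Only those with fewer than two other additional criteria are.
- A reader might apply 2.5-5% to 1437 and attach that headcount to this SAP, which covers Kazakhstan only.
- A reader might express the shift as a share of a 39% 'no' group, from the 61% with metabolic syndrome in protocol 5.1. That figure describes patients with uncontrolled BP in another study. It also conflicts with the lipid assumptions above: with two or more lipid criteria in 19-50%, some 50-81% would be 'no' before any in-range glucose is counted.

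Nor can a dilution in mm Hg be stated, since no passage gives a difference in BP change between patients with and without metabolic syndrome.

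**Conclusion.** The point holds as a defect of the printed rule. Class membership reverses as glucose rises for patients who need the glucose criterion, and patients with diabetes are divided by lipids and glucose control. It affects the metabolic-syndrome subgroup results for SBP, DBP and target BP, their between-subgroup p-values, and the reported percentage with metabolic syndrome. The overall primary estimate does not depend on it.

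The share of patients affected cannot be estimated from the documents. The 2.5-5% is an order of magnitude that depends on assumed and independent lipid prevalences, on 13% diabetes carrying over from another population, and on an assumed 50-80% above range. In the Kazakhstan analysis it is likely a handful of patients, within subgroups that SAP 2.4 and section 5 already describe as limited by sample size. It should be corrected because the remedy is cheap and determines what the yes/no contrast can support. It is not a threat to the study's main conclusion, and the documents do not show that the cited definition is itself mistaken.

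**What to change.** In a revised SAP, which protocol section 13 provides for, keep the protocol's cited definition and prespecify a second derivation. In the second, the glucose component is also met by either of:

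- diabetes recorded as a concurrent condition at V1;
- glucose above the printed upper limits, where the value can be identified as fasting or post-load.

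State that recorded diabetes counts as one additional criterion, and whether the two glucose rows may together supply both.

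Report the metabolic-syndrome yes/no subgroup tables and the percentage with metabolic syndrome under both derivations. Do not interpret a yes/no difference that appears under only one. Ask the sponsor whether the upper limits are intended; if they are not, make the uncapped version the main one.

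The cost is one extra derivation and one repeated set of subgroup tables. The diabetes clause will also move some patients whose glucose is below 6.1 mmol/L, so the two derivations may differ by slightly more than the 2.5-5% above: at most 0.13 × 0.476 ≈ 6% under the same lipid and diabetes assumptions.
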